### **4.3 Stratification**

No general stratification will be applied. Only subgroup analyses will be performed for subgroups described in Section 4.2.

## **5. Data Handling**

### **5.1 Handling of Missing Data and Outliers**

Missing data will not be imputed, and data will only be analysed as available.

During data recording and manual data checks, queries may be raised regarding implausible data. All queries will be closed prior to the hard lock of the database. The investigator will either confirm or correct the value. Subsequently, the corrected or confirmed value will be used for the analysis.

## 5.2 Handling of Data from Withdrawals and Drop-outs

Data of withdrawals and drop-outs will be used as available.

## 5.3 Handling of Multiple Comparisons and Multiple Primary Variables

Given the exploratory nature of this study, no confirmatory statistical tests are done, and no multiple comparisons will be performed.

## 5.4 Data Review

There will be no data review meeting. All open queries and issues will be resolved prior to the hard lock of the database. All open questions/discrepancies for a patient that cannot be solved (even after consultation of the corresponding investigator (if applicable)), will be provided in a list to the sponsor for a case-by-case evaluation before hardlock.

Protocol deviations will be identified in a joined effort by the Sponsor, Project Management, Data Management, Clinical Monitors and Statisticians and provided in a protocol deviation listing.

# 6. Variables for Analysis

## 6.1 Disposition

- Number of subjects enrolled
- Number of subjects who completed the study (according to protocol)
- Number of subjects who discontinued the study including the reason for discontinuation
- Number of subjects who discontinued the study for reasons associated with COVID-19
- Number of subjects per visit
- Time to discontinuation / study completion

## 6.2 Demographics and Other Patient Characteristics

The following demographic and other patient characteristics will be evaluated:

- Demographic information (race, sex, age, weight, height, BMI, educational level)

Since only the year of birth is recorded in the eCRF, the age of subjects will be calculated as follows:

$$\text{Age} = \text{Year of Visit 01} - \text{Year of birth.}$$

The BMI is automatically calculated in the eCRF as follows:

$$\text{BMI} = \text{Weight [kg]} / (\text{Height [m]})^2$$

- Time since implantation in months

$$\text{Time since implantation} = (\text{Date of Visit 01} - \text{Date of implantation} + 1) \div 30.4375$$

with 1 month counted as 30.4375 days (=360.25 days / 12 months)

- Medical history, concomitant diseases and concomitant medications
- Glaucoma medication

### 6.3 Primary Performance Variables

The following primary performance variables are planned to be evaluated:

- Limits of agreement between IOP measurements made using GAT and the ARGOS-IO system at each study visit
- Limits of agreement between IOP measurements made using DCT and the ARGOS-IO system at each study visit
- Incidences of observed device malfunctions and nature of device malfunction

### 6.4 Secondary Performance Variables

The following secondary variables are planned to be evaluated:

- Glaucoma progression over the course of the study evaluated by change in
  - visual field
  - cup/disc ratio (horizontal and vertical)
  - OCT results for the optic nerve
  - IOP
- Number of changes in glaucoma medication
- Number of unscheduled visits due to self-measured increased IOP

### 6.5 Primary Safety Variables

The following safety variables are planned to be evaluated:

- Incidences of medical device related adverse events
- Incidences of medical device related serious adverse events

- An AE is considered to be device related if there is at least a possible relationship to the medical device according to the rating of the investigator
- An AE is considered to be serious if it meets any of the criteria defined in Section 9.1.1.2 of the CIP

## 6.6 Other Variables

The following additional variables are planned to be evaluated:

- Visual acuity (BCVA, sphere, cylinder, axis) at each visit
- Score for the National Eye Institute Vision-related Quality of Life Questionnaire – VFQ-25 at the respective visit
- Device deficiencies
- External eye photography results at each visit
- Slit-lamp biomicroscopy results at each visit
- Funduscopy results at each visit
- Gonioscopy results at each visit
- Corneal endothelial cell density at each visit
- Central corneal thickness at each visit
- Comparative measurements performed in the clinic between study end of ARGOS-01/ARGOS-02 and Visit 01 (GAT vs. ARGOS-IO)
- Position of IOL and ARGOS-IO pressure sensor
- IOP self-measurements (Analysis is not part of this SAP but will be done by the Sponsor)

## 7. Statistical Analysis Methods

### 7.1 Descriptive Statistics

The default summary statistics for quantitative variables will be the number of non-missing observations (n), number of missing observations (miss), arithmetic mean, standard deviation (SD), lower quartile (Q1), upper quartile (Q3), minimum (min), median, and maximum (max) for those patients with data available.

For categorical variables, the number (n) and percentage (%) of patients per category will be the default summary presentation, and, if applicable, the number of missing values is provided in a “Missing” category. For the number of missing values, only patients that attended the respective visit will be counted. Percentages will be calculated using a denominator of all patients with non-missing data. If necessary, the denominator will be specified in a footnote to the tables for clarification.

All tables including calculation of change over time (Visit 01 vs Visit 02 – Visit 07) will also include summary tabulations for the raw values of the respective variable analysed.

In case of analyses per eye, results will be grouped by study eye / fellow eye instead of right eye / left eye.

## 7.2 Rounding Rules

### 7.2.1 Estimates of the Mean and Standard Deviation

When using actual data, the mean and standard deviation will both be calculated to at least 2 extra places than the actual data and the result will be rounded to one more decimal place than the original data.

When using derived data, i.e., data already derived from actual data, results are calculated to at least one more decimal place than these derived data and subsequently rounded to the same number of decimal places as the used values.

### 7.2.2 Other Data

Quartiles as well as the confidence interval and median will be presented with the same number of decimal places as the mean. Minimum and maximum will be presented with the same number of decimal places as the data used. For estimates of proportions, the result will be rounded to 3 decimal places. If proportions are displayed as percentage, 1 decimal place will be displayed. For example, a proportion of 0.655 will be presented in percentage as 65.5%.

## 7.3 Data Derivation

### 7.3.1 Change Over Time

Whenever the change over time is analyzed, the result at the start of the time period of interest (usually Visit 01) is subtracted from the result at the end of the time period of interest (usually Visit 02 – Visit 07)

### 7.3.2 Study Days and Durations

Study days and, if applicable and meaningful, durations will be determined by comparing the respective date to the date of the first study visit (Visit 01).

- If the respective date is on or after the date of the first study visit:  
Study day/Duration = date (e.g. date of visit) - date of first study visit + 1
- If the respective date precedes the date of the first study visit:  
Study day/Duration = date (e.g. date of medical history event) – date of first study visit

### 7.3.3 Time to Onset and Duration of Adverse Events

Time to onset and duration of adverse events will be calculated as follows:

- Time to onset = start date of AE - date of implantation of ARGOS-IO pressure sensor +1
- Duration of adverse event = stop date – onset/worsening date + 1

#### 7.3.4 Time to Discontinuation / Study Completion

Time to discontinuation / study completion will be calculated as follows:

- Time to discontinuation / study completion = date of Visit 07 / discontinuation - date of first study visit + 1

#### 7.3.5 Derivation of Other Variables

Manifest refraction spherical equivalents will be derived from their cylindrical and spherical components according to the following formula:

$$\text{MRSE} = \text{Spherical component [D]} + 0.5 \text{ cylindrical component [D]}$$

Cylindrical component (CYL) of manifest refraction can be indicated as plus CYL diopter using plus cylinder notation or alternatively, as minus CYL value at axis rotated through 90° using minus cylinder notation. Both notations are equivalent, but including both notations in the same analysis leads to incorrect estimate of mean of spherical (SPH) and of CYL variables. The conversion from one notation to the other influences also the spherical component of spherocylindrical correction. Therefore, a conversion of cylindrical component, sphere and axis are required in case data was recorded in minus notation. To convert minus into plus notation, the following formula is used:

$$\text{SPH}' = \text{SPH} + \text{CYL}$$

$$\text{CYL}' = -\text{CYL}$$

$$\text{Axis}' = \text{Axis} + 90^\circ$$

In case the resulting axis value (Axis') is greater or equal to 180°, 180° will be subtracted to determine the final axis value. No changes will be made to positive notations.

Best corrected visual acuity (BCVA) will be provided in Snellen. For preparation of summary statistics, these will be converted to logMAR according to Holladaya as follows:

- 1) Convert Snellen visual acuity to equivalent decimal acuity (e.g. 20/40 = 0.50)
- 2) LogMAR = -log(Decimal acuity)

---

a Holladay, J.T. (1997): Proper Method for Calculating Average Visual Acuity. J Refract Surg 13:388-91.

## 7.4 Evaluation of Demographics and Other Patient Characteristics

### 7.4.1 Disposition of Patients

Subject disposition will be tabulated including the numbers of subjects enrolled, number of subjects completing the study (according to protocol), number of subjects who discontinued the study (including the reason for discontinuation) and the number of subjects who discontinued the study early due to COVID-19. Percentages will be calculated based on the number of subjects enrolled in the trial, except for the tabulation of reasons for discontinuation and number of subjects discontinuing due to COVID-19, where the percentages will be based on the number of subjects who discontinued the study early.

The number of subjects attending the respective visit as well as the time to discontinuation / study completion calculated as described in Section 7.3.2 will further be tabulated. A flow-chart detailing the number of subjects at the different visits and the reason for discontinuation will be prepared.

### 7.4.2 Demographics and Other Patient Characteristics

Demographic information and other patient characteristics (i.e. age (year of birth), gender at birth, race, weight, height, BMI and educational level) will be summarized using summary statistics (N, mean, SD, median, minimum, maximum, upper and lower quartile) for continuous variables (i.e. age, weight, height, BMI, time since implantation) or absolute and relative frequencies (n, %) for categorical variables (i.e. gender at birth, race, educational level).

### 7.4.3 Medical History, Concomitant Diseases and Concomitant Medications

Absolute and relative frequencies (n, %) of medical history and concomitant diseases will be described based on MedDRA system organ class (SOC) and preferred term (PT) levels by related body system. Results will be prepared by frequency of occurrence.

Absolute and relative frequencies (n, %) of concomitant medication will be provided based on Anatomical Therapeutic Chemical (ATC) Classification code levels 2 and 3 separately for glaucoma medication and other medications. Only medications ongoing at screening or with start date during the study will be considered, all other medications will be listed only.

## 7.5 Evaluation of Primary Performance Variables

### Limits of agreement

The Bland-Altman method, which compares the mean of paired measurements to their difference, will be used to determine the upper and lower limits of agreement expected to contain 95% of the IOP value pairs obtained with the ARGOS-IO system and GAT. The agreement evaluation will follow

the publication of Zou (2011)b. Zou describes two cases, namely Case I for the assumption that the true value varies over time and Case II for the assumption that the true value is constant over time. Case I requires a pairing of measurements between devices while Case II requires no pairing. Since within each visit only one series of GAT measurements is done and GAT measurements are done consecutively followed directly by the measurements with the ARGOS-IO system, no pairing is possible, and Case II is assumed for the evaluation for data within a visit. By assumption of Case II, it is not necessary to calculate the mean of each series with the respective device, but data can be used as available for the analysis per visit. Please note that this procedure differs from the CIP since it was originally assumed that several series of measurements per visit would be available. The two-sided 95% confidence intervals for each of the agreement limits will be calculated using the Mover method to account for repeated observations. In case of the overall analysis, available data of all visits are included under assumption of Case I since it can not be assumed that the IOP is constant between visits. For this purpose, the mean of each measurement series will be calculated and used for evaluation of limits of agreement as described in the CIP. IOP values will be displayed as Bland-Altman plots of individual measurement pairs by measurement technique for each visit and overall. The limits of agreement between the ARGOS-IO system and DTC measurements will be also calculated by the described procedure.

The difference of measurements between the ARGOS-IO measurements and GAT / DTC will further be summarized per visit using descriptive statistics. The difference per subject will be calculated as the difference between mean of ARGOS-IO values and mean of GAT / DTC values of the same series (Difference = mean of ARGOS-IO values – mean of GAT/DTC values).

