7.2.4 Analysis of Primary Performance Outcome Variables

Limits of Agreement

The Bland-Altman method, which compares the mean of paired measurements to their difference will be used to determine the upper and lower limits of agreement expected to contain 95% of the IOP value pairs obtained with the ARGOS-IO system and GAT. For this purpose, the mean of each series with the respective device will be calculated and used for comparison. The agreement evaluation will be based on the assumption that the measurements are constant within the measurement series but not between measurement series with the same device. The two-sided 95% confidence intervals for each of the agreement limits will be calculated using the Mover method (Zou, 2011) to account for repeated observations. IOP values will be displayed as Bland-Altman plots of individual measurement pairs by measurement technique for each visit and overall as well as mean plots over time.

Because the ARGOS-IO implant is in direct contact with the aqueous humor and gives a digital readout of IOP, it is anticipated to objectively measure the true IOP. In comparison, although GAT is considered the gold standard, it measures IOP indirectly through applanation of the cornea and is known to be influenced by corneal thickness and biomechanical properties (Burr, et al., 2012). In addition, measurements with GAT are known to be subject to operator bias.

Consequently, the absolute IOP values obtained with the ARGOS-IO system are expected to show a systematic shift in measurements compared to those obtained from indirect methods. The Pascal

 Implantdata Ophthalmic Products GmbH	Clinical Investigation Plan ARGOS-03	Revision C Page 46 of 67
---------------------------------------------------------------------------------------------------------------------------	-------------------------------------------------------	---------------------------------

Dynamic Contour Tonometer (DCT) is constructed to alleviate some of the operator bias of GAT measurements as well as eliminate most of the corneal biomechanical influence on IOP readings. Therefore the limits of agreement between the ARGOS-IO system and DTC measurements will be also calculated by the described procedure.

Device Malfunctions

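### SAP 7.5 gives per-visit limits of agreement for single readings and overall limits for series means under one description, so the two sets are not comparable

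*SAP*

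**What the plan says.** SAP 7.5 (Limits of agreement) opens with one target for all limits: "limits of agreement expected to contain 95% of the IOP value pairs obtained with the ARGOS-IO system and GAT". DCT follows the same procedure.

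- **Per visit.** Case II (true value constant) is assumed. The SAP states that "By assumption of Case II, it is not necessary to calculate the mean of each series with the respective device" and that "data can be used as available for the analysis per visit".
- **Overall.** "available data of all visits are included under assumption of Case I", and "the mean of each measurement series will be calculated and used for evaluation of limits of agreement as described in the CIP".
- **Plots.** Within a visit "no pairing is possible", but later in the same paragraph "IOP values will be displayed as Bland-Altman plots of individual measurement pairs by measurement technique for each visit and overall".
- **Per-visit summary.** The SAP also plans descriptive statistics, per visit, of the mean ARGOS-IO value minus the mean GAT or DCT value of the same series.

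Protocol 7.2.4 had one unit throughout: "the mean of each series with the respective device will be calculated and used for comparison". SAP 7.5 and SAP 8 disclose that the per-visit method departs from this. They do not say that the quantity being estimated changes.

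**The concern.** Limits of agreement describe how far one measurement by one method may lie from one by the other, so they mean little until the measurement is defined. Here a measurement is one reading in the per-visit limits and the mean of two or three readings in the overall limits. Averaging removes part of the within-series noise. A reader who sets the two side by side cannot tell how much of any difference comes from averaging and how much from change between visits. A reader who applies the overall limits to single readings will overstate the agreement.

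The plots raise a related problem. If pairing within a visit is impossible, the text does not say what a per-visit point represents. Of the 16 Bland-Altman figures in the SAP appendix, 14 are per visit.

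**Working it through.** **Inputs**

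- Readings per series: 2 GAT (or DCT) and 3 ARGOS-IO, with a third tonometer reading if the first two differ by more than 2 mmHg (Protocol 6.4.3.2 and 6.4.4.15).
- At most 26 patients and 7 visits.
- Scale of disagreement: ARGOS-02 mean difference 2.8 mmHg, limits -1.7 and 7.4 mmHg (Protocol 4.2). The protocol does not say whether these refer to readings or series means; I take them as series-mean limits.
- Within-series SDs, sG for the tonometer and sA for ARGOS-IO: not in the documents, so assumed. The ±5 mmHg imprecision in Protocol 3.3.3 concerns repeated measurements before and after treatment and is not used here.
- The SAP does not print the Case II formula. I take its limits to refer to single readings because the readings enter unaveraged.

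The documents state no expected width for the limits, so there is no planned figure to reproduce.

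**Step 1: scale.** Half-width = (7.4 + 1.7)/2 = 4.55 mmHg. SD = 9.1/3.92 = 2.32 mmHg. The midpoint is 2.85, against a stated mean of 2.8, so the limits are symmetric to rounding.

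**Step 2: variance identity.**

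Var(single-reading difference) = Var(series-mean difference) + (1 - 1/mG)·sG² + (1 - 1/mA)·sA²

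With mG = 2 and mA = 3, series means leave out 1/2 of the tonometer and 2/3 of the ARGOS-IO within-series variance. The direction is therefore fixed whenever either variance is above zero.

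**Step 3: size.** Single-reading SD = √(2.32² + 0.5·sG² + 0.667·sA²). Coverage of single-reading pairs by the series-mean limits = 2Φ(1.96 × 2.32/SD) - 1.

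| sG | sA | Single-reading SD | Half-width (vs 4.55) | Wider by | Coverage |
|---|---|---|---|---|---|
| 0.5 | 0.25 | 2.36 | 4.62 | 1.5% | 94.6% |
| 0.5 | 0.5 | 2.38 | 4.67 | 2.7% | 94.4% |
| 1.0 | 0.5 | 2.46 | 4.82 | 6.0% | 93.6% |
| 1.0 | 1.0 | 2.56 | 5.02 | 10.3% | 92.4% |
| 1.5 | 1.0 | 2.68 | 5.25 | 15.4% | 91.0% |
| 1.5 | 1.5 | 2.83 | 5.55 | 21.9% | 89.2% |

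If the ARGOS-02 limits already refer to single readings, the identity runs the other way. For SDs of 0.5 and 1.0 in both devices, the series-mean half-width would be 4.43 and 4.03 mmHg, which is 2.7% and 11.5% narrower than 4.55.

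**Step 4: simulation.** 1,500 runs of 26 patients by 7 visits, with the third-reading rule, an assumed between-patient SD of 2.0 and an assumed patient-by-visit SD of 1.0 mmHg. Mean half-widths in mmHg:

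| sG, sA | Per-visit Case II | Per-visit series means | Overall Case I | Single-reading pairs covered by overall limits |
|---|---|---|---|---|
| 0.5, 0.25 | 4.51 | 4.44 | 4.44 | 93.7% |
| 1.0, 0.5 | 4.86 | 4.58 | 4.60 | 92.5% |
| 1.5, 1.0 | 5.60 | 4.89 | 4.91 | 90.5% |

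The overall limits agree with the per-visit series-mean limits, not with the planned per-visit Case II limits. They cover about 94% of series-mean pairs; that shortfall from 95% is a small-sample effect.

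**Step 5: drift.** With sG = 1.0, sA = 0.5 and an assumed drift of 0.5 mmHg per visit, the overall half-width is 5.00, wider than per-visit Case II at 4.86. The overall limits still cover fewer single-reading pairs (93.0%) than series-mean pairs (94.2%).

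**The case against.** **The overall limits are not a listed primary variable.** Protocol 7.1.4 and SAP 6.3 define the limits at each visit. The SAP's table list names limits by visit and by subgroup and visit only, and the overall analysis has 2 of the 16 Bland-Altman figures. This stands: the overall limits are supporting.

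**The overall result need not look better.** A reader might infer that averaging will make the overall limits narrower than the per-visit ones. The documents do not support that. The overall limits also take in change of the difference across visits, and Protocol 6.1.2 allows the sensor to be adjusted against GAT at least yearly. Step 5 shows them wider.

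**Much is already planned.** The per-visit summary of mean differences includes an SD under SAP 7.1, so per-visit series-mean limits can be derived from it. This stands. Missing are a statement of unit and any overall single-reading limits.

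**The plots may not involve arbitrary pairing.** A reader might infer that programmers must match readings at will. The plot wording is carried over from Protocol 7.2.4, where the pairs are series means, and the only per-patient difference that SAP 7.5 defines is mean minus mean. One point per patient and visit is a fair reading. The wording still conflicts with the statement that pairing is impossible.

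**The shift is modest against sampling error.** At 26 patients the approximate 95% interval around one per-visit limit is ±1.96 × 2.32 × √(1/26 + 1.96²/50) = ±1.5 mmHg. The shifts per limit for equal SDs of 0.5, 1.0 and 1.5 are 0.12, 0.47 and 1.00 mmHg. This is true, but the shift is systematic and always in the same direction.

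**Nothing is decided by it.** The study is exploratory and SAP 7.5 sets no acceptance limit. Nor can the point rest on home use: the protocol does not say that a home measurement is a single reading, and self-measurements are outside the SAP. The sensor check in Protocol 6.1.2 averages three ARGOS-IO readings, so series means have a documented use. Both units are legitimate.

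**Conclusion.** The point holds as a mismatch of unit between two correctly computed sets of limits. The per-visit limits refer to single readings and the overall limits to series means, and the SAP gives both the same description. For the same pooled data, the overall limits are narrower than single-reading limits and cover fewer than 95% of single-reading pairs whenever within-series variance is above zero. They are too narrow only if applied to single readings.

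For assumed within-series SDs of 0.5 to 1.5 mmHg in both devices, single-reading limits would be about 3% to 22% wider, and series-mean limits would cover about 94% to 89% of single-reading pairs. These sizes rest on the assumed SDs and on taking the ARGOS-02 limits as series-mean limits. They shrink if consecutive readings repeat better. The statements on pairing within a visit also need to be reconciled. It is a cheap improvement that the SAP should make.

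**What to change.** In SAP 7.5, state the unit for each set of limits and report both at each visit and overall:

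- **(a) Series means, as in the protocol.** Per visit these follow from the mean-difference summary already planned; overall they are the planned Case I limits.
- **(b) Single readings.** Per visit these are the planned Case II limits. Overall, add (1 - 1/m) times the pooled within-series variance of each device to the Case I variance, with m the harmonic mean number of readings per series, and carry the added terms through MOVER. State how series with a third tonometer reading enter m and the pooled variance.

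Replace the plot wording with one point per patient and visit: the difference of series means against their average. Draw the series-mean limits on that plot, and show single-reading limits there only if separately labelled.

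No new data are needed. The cost is SAP wording, some extra programming (mainly the added variance terms in MOVER), and overall single-reading limits somewhat wider than the series-mean limits now planned.
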